4.3. Budget

The budget is shared between the four centers and details are given in the electronic application.

4.4. Plan for activities, visibility, and dissemination

A time period of five years is scheduled for completing the entire project. Details are given in the electronic application. Results will be communicated to researchers, clinicians, patients, user organizations, and the public and politicians/decision makers. The results will be published in international journals with a high impact factor. The research project will be the basis for four PhD-theses. The results will be disseminated to other clinicians and clinics through clinical workshops and lectures, through popular papers in relevant medical, physiotherapeutic and psychological journals, communication on the e-network for Norwegian General Practitioners (Eyr), and through the Norwegian Competence Centre for Complex Symptom Disorders using information leaflets, supervision and conferences. The results will be communicated to user organizations in close collaboration with them. The results will also be communicated to the general population and politicians through articles in newspapers and specific magazines or websites. This may also include meetings with politicians and policy makers or informing the Norwegian health authorities through meetings or informational letters.

Planned scientific papers are:

1. Comparing ACT with and without enhanced mindfulness training to a patient education program: a randomized controlled trial (hypothesis 1 and 2).
2. Does mindfulness training improve attentional processes in chronic pain patients? Secondary analyses from a randomized controlled trial (hypothesis 3 and 4).

3. Are effects of ACT and mindfulness training for chronic pain mediated by changes in attentional processing? Results from a randomized controlled trial (hypothesis 5 and 6).
4. ACT for chronic pain, for whom does it work? Moderators of change in a randomized controlled trial (hypothesis 7 and 8).
5. Patient education or ACT for chronic pain? A cost-effectiveness analyses of a randomized controlled trial (hypothesis 9).
6. The long-term effects of ACT for chronic pain, a three-year follow up from a randomized controlled study (hypothesis 10).

4.5. Plan for implementation

The research consortium ensures that the research study is closely affiliated with the routine clinical practice in all four health regions. Specific researchers and specific clinicians are geographically located in each region to ensure that the recruitment, assessment and treatment of patients are conducted in accordance with the research protocol and can ensure that the study can be implemented immediately. Already in 2023 it should be possible to begin the implementation of new empirical knowledge from this research project into the routine practice of the clinics participating in the study and to offer other pain clinics and rehabilitation centers nationally and internationally, including psychiatric outpatients clinics, concrete ways of implementing this knowledge into their assessment and treatment programs. A great advantage of this research project is that it makes use of practical and specific tools and procedures which are theoretically and empirically founded in cognitive neuroscience and within modern clinical psychology and medicine which makes translation into new clinical procedures convenient.

5. User involvement

The User Committee at St. Olav's hospital has appointed [name] as the user participant to follow the research field for Department of pain and complex symptom disorders. She accepted in 2017 to be engaged in the planning process and be part of the Research Consortium that will meet four times a year (see paragraph 4.2 above). She proposed that one of the groups should be mindfulness training, which was accepted. She got the first draft at the same time as the other partners and thereafter she was part of a planning meeting. Besides inclusion of an active user participant in the Research Consortium monitoring the study, "The Norwegian society for chronic pain patients" has been informed with an overview of the project in Norwegian, and their leader [name] has responded positively. During the project period four additional user representatives, one in each region, will be selected by User organizations. They will be involved in all stages of planning and implementation as well as during results analyses and results communication. These four representatives will have formal meetings with the Research Consortium and members of the Scientific network group at treatment start and each spring and each autumn during the entire project period.

6. Ethical considerations

## Section 2: Introduction

### 2.1 Background and rationale

Numerous population-based surveys have presented surprisingly high prevalence figures of chronic pain (Steingrimsdottir et al., 2017) and a pooled prevalence of 31% worldwide (Steingrimsdottir et al., 2017). As non-pharmacological alternatives, psychosocial treatments have been recommended for chronic pain management (Jensen, 2011). One such treatment is Acceptance and Commitment Therapy (ACT). (Ost, 2014). Among patients with chronic pain, several small clinical trials have shown that ACT is superior to controls in terms of increasing function and improving mental health, with small to medium effect sizes (Hughes et al., 2017). However, further methodologically robust trials are required (Veehof et al., 2011). The primary aim of this study is thus to examine in a large sample of patients from four multidisciplinary pain centers whether ACT for chronic pain is more effective than a patient education program, and whether adding daily mindfulness training will improve the outcome.

### 2.2 Objectives

The primary aim of the study is to investigate the effectiveness of ACT and whether adding a component of mindfulness training will improve outcomes on pain (primary outcome), attentional functioning, physical functioning and mental health (secondary outcomes), compared to a control group receiving an educational program. A secondary aim is to assess the degree to which improvement in attentional functioning can act as a mechanism of change (mediator) in pain. A third aim is to identify patient characteristics (phenotypes) that predict treatment effects (moderators of change), or, equally important, that predict failure to achieve benefit.

## Section 3: Study Methods

### 3.1 Trial design

The Study is designed as a multi-centre RCT where patients with chronic pain lasting longer than 6 months who are referred to a multidisciplinary pain clinic at either Oslo University Hospital, St Olavs University Hospital, Haukeland University Hospital or is the University Hospital of North Norway are included in three parallel groups; ACT; ACT with enhanced mindfulness or education group. This is a group treatment lasting over 8 weeks, where one session lasts four hours. Patients will be in groups of up to 10 patients.

### 3.2 Randomization

Randomisation is performed as a block randomisation where each treatment centre included up to 24 patients and randomised them into one of the three groups. Randomisation was performed by a web-based randomisation system (Web Case Report Form; WebCRF) developed and administered by Unit of Applied Clinical Research, Faculty of Medicine and Health Sciences, NTNU, Trondheim, Norway. This unit is not otherwise involved in the trial management or trial conduct.

### 3.3 Sample size

The sample size calculations are described in detail in the registered protocol. We calculated sample size based on an assumption of a mean baseline average pain intensity of 5.4 with a standard deviation of 2.1 (Thong et al., 2018) and a 10% reduction in pain intensity in the education group, 20% in the ACT group and 30% in the ACT with mindfulness training

group. These improvements may be regarded as minimally important vs moderate changes, respectively (R. H. Dworkin et al., 2008; Farrar et al., 2001). For a two-sided test with 5 % significance level and 80% power, we calculated that the number of patients needed to compare ACT with mindfulness to the education group was 58 in each group. Comparing ACT with and ACT without mindfulness training would require 141 in each group, and comparing ACT without mindfulness training to education would require 126 in each group. We increased group size to 162 participants per group to allow for dropout, to provide equality between groups and for secondary analyses.

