4. The four centers have a response rate on internet-based self-report on almost 100% pre-admission and about 80% one year after treatment from four identical online quality records. This self-report system will be used in the study and has been published as feasible by our research group (34).
5. It should be possible to identify patient characteristics (phenotypes) that can guide clinicians in the future in the selection of which of the patients are likely to profit from ACT, and which patients are likely to receive benefits from the addition of mindfulness training.
6. It should also be possible to identify patients who benefit less from the treatments and who may need other alternatives. Patient characteristics can help us to identify key target components in the development of new treatments for these patients.
7. The theoretical hypothesis aiming to identify a key mediator of change is based on modern cognitive neuroscience including thorough neurobiological studies of the human brain.
8. Both for self-report measures and attentional functioning the study will use safe computerized test systems the patients can complete in their homes. This will make it possible to increase the number of assessments without the subjects needing to return to the outpatient clinic. This will increase the quality of assessments and reduce the cost
9. Since the study includes self-report assessment methods that are easy to deliver and score, it is also easy to translate the knowledge and procedures to other treatment facilities in Norway and internationally after the project period.

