4.1 Project arrangements, method selection and analyses

4.1. 1. Sample

At least 486 patients will be included in the study (see power analyses below). Patients will be included if they are referred to one of the pain clinics with a primary diagnosis of chronic pain lasting for at least six months. About 200 patients will be recruited from Oslo, 200 from Trondheim, 100 from Bergen, and 100 from Tromsø. Exclusion criteria will be severe somatic disease or severe mental disorder (ongoing mania, psychosis, suicidal ideation or substance abuse/addiction). In addition will patients who cannot communicate in Norwegian or who need 24-hour personal assistance be excluded. Each treatment center will randomize the patients into three different research programs (see below).

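### The stated 80% power is not supported: 141 and 126 per group do not follow from the stated inputs, and 162 per group covers only 13% loss against 141

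*SAP*

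**What the plan says.** SAP 3.3 and the protocol section on statistical power (the second section numbered 4.1.5) carry the same calculation. The inputs are a "mean baseline average pain intensity of 5.4 with a standard deviation of 2.1" and a "10% reduction in pain intensity in the education group, 20% in the ACT group and 30% in the ACT with mindfulness training" group. The error rates are given by "For a two-sided test with 5 % significance level and 80% power".

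Three needs follow: 58 per group for ACT with mindfulness against education; "Comparing ACT with and ACT without mindfulness training would require 141 in each group" (hypothesis 2); and "comparing ACT without mindfulness training to education would require 126 in each group" (hypothesis 1). The group size is then set: "We increased group size to 162 participants per group to allow for dropout, to provide equality between groups and for secondary analyses". No dropout rate is given.

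The only retention figure in either document is in the protocol's Introduction, in the fourth of the listed strengths. The centres' online quality records have a response of "about 80% one year after treatment", and the same self-report system is to be used in the trial. SAP 3.6 places the main outcome at 52 weeks.

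On total size, protocol 4.1.1 gives 486 as a minimum, and 4.1.2 gives 162 per group. Section 4.1.1 also says: "About 200 patients will be recruited from Oslo, 200 from Trondheim, 100 from Bergen, and 100 from Tromsø".

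**The concern.** The reductions of 10%, 20% and 30% are equally spaced, so ACT against education and ACT with against without mindfulness rest on the same difference and the same SD. Under one method they must need the same number, yet the plan gives 126 and 141. With equal groups, the design must also meet the larger need after losses, and the step from 141 to 162 looks small beside a one-year response of about 80%.

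What is at stake is interpretation. Recruitment ended in April 2023 (SAP 5.2), so the plan can no longer change the sample size. A null result for ACT alone, or for added mindfulness, would be read against a claimed 80% power that the stated figures do not deliver.

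**Working it through.** **Inputs.** From SAP 3.3: mean 5.4, SD 2.1, two-sided 5%, 80% power, reductions 10/20/30%, stated needs 58/141/126, planned 162 per group. From the protocol's Introduction: about 80% response at one year. From protocol 4.1.1: minimum 486 and the centre targets.

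**Step 1: assumed differences.** Group means are 5.4 × 0.9 = 4.86 (education), 5.4 × 0.8 = 4.32 (ACT) and 5.4 × 0.7 = 3.78 (ACT with mindfulness). The differences are 0.54, 0.54 and, between the outer groups, 1.08.

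**Step 2: reproduce the stated needs.** n per group = 2 × (1.960 + 0.842)² × (SD/difference)², where (1.960 + 0.842)² ≈ 7.849.

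| Comparison | Difference | Computed n | Stated n |
|---|---|---|---|
| ACT with mindfulness vs education | 1.08 | 59.4, so 60 | 58 |
| ACT with vs without mindfulness | 0.54 | 237.4, so 238 | 141 |
| ACT vs education | 0.54 | 237.4, so 238 | 126 |

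The 58 comes within two patients, and exactly if the means are rounded to 4.9 and 3.8. That points to a plain comparison of two means. The other two figures do not reproduce. Variants tried for 141 and 126, in that order:

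- one-sided test: 188 and 188
- t-test: 239 and 239
- means rounded to one decimal: 277 and 193
- SD shrinking in proportion to the mean: about 135 and 173
- baseline adjustment, n × (1 − r²): needs r of about 0.64 for 141 and 0.69 for 126, but 0.18 for 58, so no single correlation explains the set

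An SD of 1.5 with a difference of 0.5 gives 141.3, and an SD of 1.7 with a difference of 0.6 gives 126.0. Neither SD is in the documents.

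**Step 3: power on the stated inputs, unadjusted.** Power = Φ(difference / (SD × √(2/n)) − 1.960).

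- n = 162: 0.54/0.2333 = 2.314; Φ(0.354) = 64%.
- n = 129.6: 0.54/0.2609 = 2.070; Φ(0.110) = 54%.

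**Step 4: the dropout margin, taking 141 at face value.**

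- Loss absorbed: (162 − 141)/162 = 13.0%.
- Remaining at 80%: 162 × 0.80 = 129.6, about 11 below 141 but above 126 and 58.
- Number that would keep 141 at 20% loss: 141/0.80 = 176.3, so 177 per group.
- Power if the stated n gives 80%: Φ(2.802 × √(remaining/stated) − 1.960). For hypothesis 2, √(129.6/141) gives 76.6%. For hypothesis 1, √(129.6/126) gives 81.1%.
- Hypothesis 2 over a range of loss: 10% loss, 81.3%; 15%, 79.1%; 20%, 76.6%; 25%, 73.9%.

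**Step 5: baseline adjustment.** The documents give no correlation, so r is an assumption here. SD becomes 2.1 × √(1 − r²), and the detectable difference at 80% power is 2.802 × SD × √(2/n), with n = 129.6.

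| Assumed r | Power for 0.54 | Detectable difference |
|---|---|---|
| 0 (unadjusted) | 54% | 0.73 |
| 0.5 | 67% | 0.63 |
| 0.6 | 73% | 0.58 |
| 0.7 | 83% | 0.52 |

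**Step 6: centre targets.** 200 + 200 + 100 + 100 = 600, or 200 per group and 160 after 20% loss. That meets 141, but not 238.

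**The case against.** Most of the case on the other side concerns dropout, and much of it stands. The 80% is a response rate in routine records one year after treatment, whereas the trial endpoint is 52 weeks from the start of treatment, in consented participants. It is a reasonable proxy, not an assumption the plan makes, and at 13% loss or less 141 is kept. Protocol 4.1.1 makes 486 a minimum, and its centre targets would leave 160 per group at 20% loss. The primary model uses every available visit with a pooled baseline (SAP 4.3 and 6.2), and SAP 3.6 cites the gain in power from repeated measures. Counting only patients observed at week 52 therefore understates the information. With an assumed r of 0.7, power at 130 per group exceeds 80%.

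Three stronger readings are tempting, and the documents do not support them.

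- **Dropout brings power down to 54%.** The fall from 80% to 64% is present at 162 with nobody lost; it comes from 141 and 126 not matching their inputs. On the plan's own needs, 20% loss costs hypothesis 2 about 3.4 points and leaves hypothesis 1 above 80%.
- **Dropout is not allowed for at all.** Some is: 13% against 141 and 22% against 126 (1 − 126/162).
- **The trial is certainly underpowered.** That depends on the baseline correlation, which is not given.

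What the objection does not reach is the first defect. The stated calculation neither invokes nor quantifies baseline adjustment or repeated measures, and no single correlation yields all three stated needs.

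**Conclusion.** The point holds in two parts of unequal weight. The larger is that 141 and 126 do not follow from a 0.54-point difference with SD 2.1, which needs 238 per group. On those inputs, unadjusted power for hypotheses 1 and 2 is about 64% at 162 per group and 54% at 130. The comparison of ACT with mindfulness against education is sound, since its 58 nearly reproduces.

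The smaller part is the dropout margin. Accepting 141, the group size tolerates 13% loss. At about 20% loss, power for hypothesis 2 alone slips to about 77%. This rests on the routine-record response as a proxy, on 162 rather than about 200 being randomised per group, and on no credit for earlier visits.

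Raising the size to 177 per group would repair only the second part; it would not give 80% unadjusted power on the stated inputs. The arithmetic is firm. The power actually achieved is uncertain, because it depends on a correlation and a retention rate that the plan does not state.

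**What to change.** Rewrite the sample-size paragraph in SAP 3.3 and carry the same correction to the protocol's power section:

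1. State the SD or baseline correlation behind 141 and 126, or replace both with figures that follow from the stated inputs.
2. State the assumed dropout rate and its source, and say that 162 covers 13% loss against 141.
3. Restate power or the detectable difference for hypotheses 1 and 2 at about 130 per group: 0.73 points unadjusted, or about 0.63, 0.58 and 0.52 at assumed correlations of 0.5, 0.6 and 0.7. Note that the mixed model recovers part of the loss.
4. Reconcile the minimum of 486 with the centre targets of about 600, and give the number actually randomised.

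The cost is a paragraph of text. No patients are added and the analysis does not change. The downside is that the stated power becomes less favourable.

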### 3.4 Framework

The MUST study is a superiority RCT assessing the effectiveness of the ACT and ACT with mindfulness compared to an active control group for people with chronic pain referred to one of four regional multidisciplinary pain clinics.

### 3.5 Interim analyses and stopping guidance

As serious adverse events are unexpected, no interim analysis or a priori defined stopping rules were defined or implemented for this trial.

### 3.6 Timing of outcome assessment

The primary and secondary outcome variables were assessed at baseline and at post-treatment, eight weeks, 16 weeks, 32 weeks and 52 weeks. This allows analyses of repeated measures on both primary and secondary outcomes, and thus increased statistical power compared to outcomes assessed at a single time-point. The main outcome of the study is pain intensity measured by BPI at 52 weeks follow-up.

## Section 4: Statistical Principles

### 4.1 Confidence intervals and P-values

The precision of the estimated effects of the interventions will be assessed by a 95% confidence interval, and the effect will be described as a point estimate (mean difference or odds ratio) with accompanying confidence limits.

### 4.2 Adherence and protocol deviations

we will define adherence to the intervention as participating on at least 4 out of the eight group sessions. Both intention to treat and per protocol analyses will be conducted.

### 4.3 Analysis populations

The primary analysis will estimate mean difference and 95% confidence interval (CI) in BPI pain intensity score at post-treatment and 52-week follow-up between the two interventions and the active control group (ACT, ACT with enhanced mindfulness and education group). The analyses will be conducted according to the intention-to-treat principle using a linear mixed model for repeated measures. This model includes all available data for all participants at each time point (i.e. baseline, post-treatment, 16 weeks, 32 weeks and 52 weeks). The distribution of the BPI pain intensity score will be assessed, and the variable may be transformed (e.g. log transformation) to better fit with the assumptions for the regression analyses. In the regression model, individual participants will be specified as a random effect, accounting for the within subject covariance structure. The effect of group and time will be specified as fixed effects using a joint variable of intervention and time. Here, baseline levels are pooled over the three study groups assuming that any baseline differences are due to

chance; this also controls for any baseline differences in the outcome variable. The between group difference at 52-week follow-up will be adjusted for the variable used for stratification in the randomisation (i.e., center). Further adjustment for baseline levels of potentially important prognostic factors will also be conducted. We will also use GEE analyses to estimate an odds ratio (with 95% CI) for a two-point change in BPI between the groups taking into account the repeated observations. This analysis will be adjusted for the same factors as those included in the linear mixed model. In addition to the intention to treat analyses, we will conduct per protocol analyses using information on adherence to the trial.

All secondary outcomes will be analysed using a similar approach; for continuous we will use linear mixed models to estimate mean differences between groups, and for ordinal or binary variables we will use logistic GEE analyses to estimate odds ratios. For analyses of mean differences, the distribution of each outcome variable will be assessed to inform possible transformation or initiate alternative analytical procedures. The precision of all estimated effects will be assessed by a 95% CI.

Possible modifiers and mediators of the effect of intervention on the primary and secondary outcomes will be assessed in secondary analyses.

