4.1.4 The intervention groups

ACT (group 1) will follow a manual based on the work of Steven Hayes and colleagues (10). The manual is adapted to a group therapy setting and includes all the dynamic processes of ACT; committed action, values, self as context, presence in the moment, defusion and acceptance. It has previously been piloted and applied to a work rehabilitation setting by our research group (39). Two qualified therapists will lead every treatment session.

ACT with enhanced mindfulness training (group 2): ACT will be performed exactly as group 1, but in addition mindfulness exercises will be introduced in the ACT sessions and patients will receive audio recordings to aid practice daily at home. The home meditation exercises session will take from 10 to 30 min. and will be based on the program developed by Kabat-Zinn (27).

The education program (group 3) aimed at improving self-management and social identification, will constitute the control group (40). Participants will receive information on relevant topics including pain and symptom management, stress, sleep, eating habits, mental health problems, communication skills and physical activity by a qualified health professional. They will have the opportunity to discuss their thoughts and experiences with the other patients in the group with the aim of strengthening social identity and support, which in turn is expected to foster more healthy management (41). This is regarded as a relevant control group because self-management programs may be cost-effective alternatives to other treatments, with likely effects on psychological well-being, but not on pain and disability (42).

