4.1.5 Organization of the groups

The two active treatment programs and the education program all consist of eight four-hour group sessions (eight subjects) during an eight-week period. All therapists will before they are considered qualified receive clinical training within the specific treatment modality during a three month period including two 2-day workshops led by a certified trainer in each field. Each treatment session will be videotaped. A random selection of videotaped sessions will be scored by two experts to establish treatment variance, treatment adherence and treatment competence. Inter-rater reliability will be assessed.

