### 6.2 Analyses methods

The primary analysis will estimate mean difference and 95% confidence interval (CI) in BPI pain intensity score at 52-week follow-up between the two intervention groups and control group (i.e., ACT vs. ACT with enhanced mindfulness or education). The analyses will be conducted according to the intention-to-treat principle using a linear mixed model for repeated measures. This model includes all available data for all participants at each time point (i.e. baseline, post-treatment, 8 weeks, 16 weeks, 32 weeks and 52 weeks). Further adjustment for baseline levels of potentially important prognostic factors, such as age, sex, socioeconomic status, pain duration, and pain intensity will also be conducted.

All secondary outcomes will be analysed using a similar approach; for continuous (or approximately continuous) we will use linear mixed models to estimate mean differences between groups, and for ordinal or binary variables we will use logistic GEE analyses to estimate odds ratios.

Possible modifiers of the effect of intervention on the primary outcome will be assessed in supplementary analyses stratified by sex, age groups, socioeconomic status, and accompanied by tests of statistical interaction to assess departure from additive effects (i.e., including a product term of group and modifier in the regression model).

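### The planned models ignore clustering by therapy group, so the 95% CIs are too narrow if outcomes vary between groups within an arm

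*SAP*

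**What the plan says.** The three programmes "all consist of eight four-hour group sessions (eight subjects) during an eight-week period" (Protocol 4.1.5, Organization of the groups). SAP 3.1 allows up to 10 per group. SAP 3.2 describes centre blocks of up to 24 patients randomised over the three arms, which implies about eight per arm in each block.

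In the primary mixed model of SAP 4.3, "individual participants will be specified as a random effect, accounting for the within subject covariance structure". The 52-week contrast "will be adjusted for the variable used for stratification in the randomisation (i.e., center"). The responder analysis is a GEE giving an odds ratio "for a two-point change in BPI between the groups taking into account the repeated observations". Secondary outcomes follow the same approach. SAP 6.2 restates the model, and the further adjusters it gives as examples are all patient characteristics.

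SAP 3.3 (and Protocol 4.1.5, Statistical power) raises the arms to 162 for attrition, equal arms and secondary analyses. Clustering is not among the reasons. Neither document has a term for therapy group or block, a cluster-robust variance, an ICC or a design effect.

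**The concern.** Patients in one therapy group share leaders, sessions and each other, so their outcomes may be alike. Each group receives one arm's programme, so variation specific to the group goes straight into the arm contrast. A participant random effect handles repeated measures within a person, not likeness between people. Four centres cannot stand in for about 20 groups per arm.

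Variation shared by a whole block behaves differently. Each block feeds all three arms, so it cancels from the contrast.

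The protocol treats delivery as something that can vary: recorded sessions are to be "scored by two experts to establish treatment variance, treatment adherence and treatment competence". For ACT, "Two qualified therapists will lead every treatment session". If group-specific variation exists, the standard errors of the primary and secondary contrasts are too small, and chance differences between therapy groups can be reported as treatment effects.

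**Working it through.** **Inputs from the documents.** Group size m = 8 (protocol), up to 10 (SAP 3.1), 24/3 = 8 (SAP 3.2). 162 per arm, so 162/8 ≈ 20 groups. SD 2.1, baseline mean 5.4 and reductions of 10/20/30% (SAP 3.3), so arm differences of 0.54 and 1.08 points. About 80% one-year response in the clinics' existing registers (protocol Introduction, strengths list), so 6.4 per group and 129.6 per arm.

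**Assumptions.** Group-specific ICC of 0, 0.01, 0.05 or 0.10 of total variance; within-person correlation r = 0.6 or 0.4.

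**1. The plan's own figures.** n = 2[2.1(1.96 + 0.84)/δ]² gives 60 per arm for δ = 1.08 (stated: 58) and 238 for δ = 0.54 (stated: 141 and 126). The stated numbers lie below the unclustered ones, so no design effect is hidden in them. The gap between 238 and 141 or 126 is a separate matter.

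**2. Simple formula.** DE = 1 + (m − 1)·ICC; type I error = 2[1 − Φ(1.96/√DE)]. Example: m = 8, ICC 0.05 gives DE = 1.35 and 9.2%; 162 patients count as 162/1.35 = 120.

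| Patients per group | ICC 0 | 0.01 | 0.05 | 0.10 |
|---|---|---|---|---|
| 8 | 5.0% | 5.8% | 9.2% | 13.3% |
| 10 | 5.0% | 6.0% | 10.4% | 15.5% |
| 6.4 (80% response) | 5.0% | 5.6% | 8.2% | 11.4% |

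**3. Baseline-adjusted contrast at week 52, m = 8.** Let s_g be the group-specific and s_b the block-shared variance, total variance 1. The true variance is proportional to (1 − r²) + 7s_g − s_b; the plan's is proportional to (1 − r²). Example: r = 0.6, s_g = 0.05, s_b = 0 gives (0.64 + 0.35)/0.64 = 1.547.

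| Case (s_b = 0) | ICC 0 | 0.01 | 0.05 | 0.10 |
|---|---|---|---|---|
| r = 0.6, undiminished | 5.0% | 6.3% | 11.5% | 17.6% |
| r = 0.4, undiminished | 5.0% | 6.0% | 10.0% | 14.8% |
| r = 0.6, group variance halved | 5.0% | 5.6% | 8.2% | 11.5% |
| r = 0.6, one fifth left | 5.0% | 5.3% | 6.3% | 7.6% |

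**4. Shared block variation (r = 0.6, s_g + s_b = 0.05).** Type I error is 11.5% at 0.05 + 0, 7.8% at 0.025 + 0.025, 5.5% at 0.01 + 0.04 and 4.8% at 0.005 + 0.045. By this formula the break-even is s_b = 7s_g.

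**5. Simulation of the repeated-measures model.** 6,000 null trials per setting; 20 blocks × 3 arms × 8 patients; five time points; pooled baseline; REML with Satterthwaite degrees of freedom; centre not simulated; simulation error about 0.3 points. Type I error:

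| s_g / s_b | SAP model | Group term only | Group + random block |
|---|---|---|---|
| 0 / 0 | 5.2% | 4.6% | 4.8% |
| 0.01 / 0 | 6.0% | 4.5% | 4.8% |
| 0.05 / 0 | 13.3% | 5.2% | 5.7% |
| 0.10 / 0 | 20.8% | 5.0% | 5.3% |
| 0.025 / 0.025 | 8.4% | 2.8% | 4.9% |
| 0.005 / 0.045 | 5.7% | 1.6% | 4.7% |

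The SAP model exceeds the formula because its participant intercept absorbs part of the group and block variance.

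A second simulation used r = 0.5, centre adjustment, block variation already present at baseline and 1,500 runs per setting. Coverage of the planned 95% CI was 94.8%, 93.5%, 89.0% and 84.6% at ICC 0, 0.01, 0.05 and 0.10. At exactly seven-fold block variance (0.02 + 0.14) it was still 93.1%.

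**6. GEE.** 20,000 null trials per setting; week 52 only; independence working model; assumed 31% responders. In the order of the table above:
- Patient-level robust variance: 4.8, 5.4, 7.6, 11.2, 6.1, 4.5%.
- Clustered on therapy group (t, 38 df): 4.8, 4.8, 4.5, 4.9, 3.6, 2.5%.
- Clustered on block (t, 19 df): 4.8, 4.8, 4.6, 4.8, 4.8, 4.7%.

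**7. Power for 0.54 points once group is allowed for (r = 0.6).** Φ(0.54/(2.1√[(2/162)(0.64 + 7s_g)]) − 1.96) = 82%, 78%, 64%, 52% at the four ICCs. With 80% response (n = 129.6, 5.4s_g in place of 7s_g): 73%, 70%, 58%, 48%.

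**The case against.** The strongest reply is that the harm depends on inputs nobody has stated. The documents give no ICC, and the large figures need 0.05 to 0.10, mostly group-specific and undiminished. SAP 3.6 puts the main outcome at week 52, 44 weeks after an eight-week course ends, and a faded group effect leaves little inflation. That stands as a limit on size. It does not cover the post-treatment contrast, which SAP 4.3 also names in the primary analysis, or the secondary outcomes.

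The block design gives real protection against shared variation, but only when that variation is many times the group-specific part. The seven-fold break-even belongs to the closed formula; in both simulations the planned model stayed anti-conservative at or beyond it.

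Manuals and therapist training may limit variation between groups; nothing shows that they remove it. The protocol evidence is only suggestive. The statement about two therapists is in the ACT paragraph, and the variance to be scored on video is not defined. The education programme is described as a type "with likely effects on psychological well-being, but not on pain and disability", which concerns mean effects and says little about an ICC for pain.

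Recruitment is complete (SAP 5.2), so the missing design effect can no longer change the sample size, and the power figures serve interpretation only.

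**Conclusion.** The concern holds. The plan models no correlation between patients treated in the same therapy group, in any arm, for any outcome. The direction follows from the design: group-specific correlation makes the planned intervals too narrow unless much larger block variation shared by the arms offsets it.

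The size is unknown. Over the assumed ICCs of 0.01 to 0.10, with no shared block variation, the closed-form type I error at week 52 runs from 5.3% (ICC 0.01, one fifth of the group variance left) to 17.6% (ICC 0.10, undiminished, r = 0.6). Simulation of the planned model reaches 20.8%. At an ICC of 0.01 the effect is minor. Confidence is high for the omission, not for any one of these figures. Since the plan neither estimates the correlation nor protects against it, and the repair is cheap, the SAP should be changed before the outcomes are analysed.

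**What to change.** **Mixed models, primary and secondary.** Add a random effect for therapy group as assigned, acting after baseline, together with an effect for randomisation block (intake cohort within centre). Both are needed: a group term alone counts variation shared by the arms as contrast error and makes the intervals too wide (type I error 1.6% to 2.8% in the two shared-variation settings). Use REML with Kenward-Roger or Satterthwaite degrees of freedom.

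**GEE.** Use a small-sample-corrected variance clustered on therapy group, or on block. A block contains all three groups, so clustering on it also avoids counting shared variation.

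**Reporting.** Give the therapy-group ICC with its CI for the primary outcome.

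**Cost.** A few lines of SAP text and Stata code, provided block and therapy-group identifiers exist. SAP 3.2 implies that therapy group is arm within block, so the randomisation record may supply both, but the documents do not say so. If the true ICC is zero, the simulated group-plus-block model widens the interval by 2.3% (five time points, complete data); a week-52-only model with fixed blocks and 20% loss widens it by 8%. If the group effect fades, a constant post-baseline term is conservative: with an ICC of 0.05 falling to one fifth, type I error is 3.7%, against 6.8% when group is ignored.
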